Prior to the visit, subjects will be asked to abstain from food or drinks for 4 hours before the procedure. These procedures will be performed on a Philips Gemini 64TF scanner at the Colorado Translational Research Imaging Center (C-TRIC). Each study visit will take approximately 2 hours. The subject will be comfortably positioned in a chair. An intravenous catheter will be inserted using standard aseptic technique. A 10-15 mCi intravenous injection of ^{11}C -PiB will be administered. The subject will be placed on the scanning table and moved into the scanner. A preliminary, 3-5 minute head CT scan will

precede the PET scan to aid in alignment and calibration, and adjust for attenuation effects. ¹¹C-PiB PET images will be acquired for approximately 20 minutes. The IV catheter will be removed at the conclusion of the study and materials will be disposed of in biohazard containers or decay chambers until they can be safely disposed.

Indications and Usage

Pittsburgh Compound B (¹¹C-PiB) is a radioactive imaging agent for Positron Emission Tomography (PET) imaging of the brain to estimate β -amyloid neuritic plaque density in adult patients with cognitive impairment who are being evaluated for Alzheimer's Disease (AD) and other causes of cognitive decline. A negative ¹¹C-PiB scan indicates sparse to no neuritic plaques, and is inconsistent with a neuropathological diagnosis of AD at the time of image acquisition; a negative scan result reduces the likelihood that a patient's cognitive impairment is due to AD. A positive ¹¹C-PiB scan indicates moderate to frequent amyloid neuritic plaques; neuropathological examination has shown this amount of amyloid neuritic plaque is present in patients with AD, but may also be present in patients with other types of neurologic conditions as well as older people with normal cognition. The use of Pittsburgh Compound B has become a widely accepted amyloid imaging method in human subjects research. As of 2008, PiB imaging was being performed at over 38 sites worldwide and had become a part of the Alzheimer's Disease Neuroimaging Initiative (48). Therefore, it has substantiated potential as a quantitative imaging biological marker for detecting amyloid plaques in subjects.

Mechanism of Action

Pittsburgh Compound B (¹¹C-PiB, or N-methyl-[¹¹C]-2-(4'-methylaminophenyl)-6-hydroxy-benzothiazole) is an ¹¹C-labeled positron emission tomography (PET) imaging agent that binds with high affinity to the amyloid- β (A β) peptide fibrils that constitute amyloid plaques, and maps on to amyloid deposition in post-mortem studies (49). Klunk and colleagues developed a number of derivatives of Congo Red, a known beta-sheet binding molecule (50). These derivatives were made lipophilic so as to be able to cross the blood brain barrier after intravenous injection and could be shown to be non-toxic. Similarly, uncharged derivatives of thioflavin T were also shown to bind amyloid *in situ* (51). Klunk and colleagues were able to demonstrate strong target engagement of the radiotracer (i.e. sensitivity), and cross-labeling studies further demonstrated that ¹¹C-PiB does not label structures that do not also preferentially label amyloid specific dye (i.e. specificity). Comprehensive toxicology tests were conducted on pre-clinical models, including tests of acute vascular irritation in rabbits, bacterial reverse mutation assay, *in vitro* mammalian cell gene mutation test, mammalian erythrocyte micronucleus test, *in vitro* mammalian chromosome aberration test, expanded acute intravenous toxicity study in rats, an expanded acute toxicity study in dogs, an evaluation of the cardiovascular and pulmonary effects in dogs, a bridging study on the acute intravenous toxicity of ¹¹C-PiB in rats, and a bridging study on the cardiovascular and pulmonary effects in dogs. Based on these studies, no deleterious toxicology results have been noted in animals.

Early clinical research studies with humans demonstrated significant and consistent ¹¹C-PiB retention in frontal cortex, precuneus/posterior cingulate, striatal, temporal, and parietal cortices in the brains of patients diagnosed with AD dementia relative to healthy controls. ¹¹C-PiB was reported in 2004 as successfully able to bind to amyloid and thus remain in the brain of AD patients, while quickly clearing the brain of normal subjects (49). These findings were subsequently confirmed in other studies (52-54), with the retention pattern consistent with the cortical distribution of neuropathological findings of A β plaques on autopsy (55), suggesting that *in vivo* imaging of amyloid deposition parallels the underlying neuropathology. Since then, many studies have reported on the use of PiB for safely imaging amyloid in AD brain by PET, and the compound has become the method of choice for longitudinal studies of amyloid development in AD and for demonstrating and quantitating the efficacy of amyloid-reducing therapies (56).

Radiation Exposure

Any exposure to radiation carries a very small risk of causing damage to tissues and the possibility of triggering a new cancer. However, the amount of radiation that each subject will be exposed to per (¹¹C-PiB) PET scan is similar to the amount received from natural sources, such as the sun (background radiation) over the course of living in Denver for approximately 1 year. We will perform PET imaging at the screening visit and at the first follow-up visit, or within a week thereof, depending upon scheduling availability. Our administered dose of (¹¹C-PiB) will be 10-15 mCi. For a (¹¹C-PiB) dose of 15 mCi (555 MBq), the expected whole body effective dose is 2.9 mSv. In addition, the effective dose for a loose dose head CT performed for localization and attenuation correction as part of the standard brain PET/CT protocol is 0.6 mSv. Thus, with two (¹¹C-PiB) scans, we expect the trial subjects to be exposed to about 7 mSv, well below the 50 mSv maximum annual dose of radiation exposure. At the first screening visit, subjects and/or subject's partner/caregiver will be asked to provide information whether the subject has been exposed to radiation during the past year (e.g. prior X-ray, CT, PET scans, etc.), so that the Study Physician and/or the Nuclear Medicine Imaging Professional can determine whether there will be a risk of the subject exceeding maximum allowed levels of radiation exposure.

RANDOMIZATION AND MAINTENANCE OF BLIND

The drug will be purchased with funds for this study and study participants will not be billed for study related costs. At the UCD site, the Leukine[®] and the placebo samples for injection will be prepared by the UCH Pharmacy, which has policies and procedures in place that describe randomization and blinding. Briefly, the pharmacy has built and implemented an Excel spreadsheet that produces random number sets which may be used for simple, weighted, block (two, four, or six sized), and stratified randomization. For blinding, the pharmacy staff includes the pharmacist manager and technician. The pharmacy staff has been involved in several clinical trials which require double blinding, and double dummy. The pharmacy is an independent entity, and has the ability to ensure and maintain blinding in any regard so that the staff at the Alzheimer's Clinic will not know which study participants are receiving the study drug or the placebo.

At the USF site, the Leukine[®] and the placebo samples for injection were randomized, prepared, and supplied to the USF Health Byrd Alzheimer's Institute's Comprehensive Clinic by the USF College of Pharmacy Manager of the Investigational Research Pharmacy, which is located within the Carol and Frank Morsani Center for Advanced Healthcare, and which is a component of USF's Clinical and Translational Research Institute (CTSI).

DATA SAFETY MONITORING PLAN AND PROTECTION OF HUMAN SUBJECTS

Because of the extensive safety history of Leukine[®] in elderly patients, we do not anticipate any serious safety problems, but we must be vigilant in assessing safety. A review of published adverse events for GM-CSF and the Genzyme Leukine[®] Product Insert and the papers it references will be used to guide the safety monitoring protocol ([38], attached as Appendix D). The greatest safety concern noted with Leukine[®] is excessive leukocytosis. Therefore, as advised by Sanofi/Genzyme Corporation, we will obtain a CBC with differential twice a week during treatment and the dosage will be reduced by half if total ANC rises above 20,000/mm³. In addition, the DSMB described below will monitor laboratory results, the MRI and the cognitive assessments for any indications of toxicity. Following are the abbreviated categories of the National Cancer Institute's (NCI) graded toxicity protocol used by Daud et al., 2008 for assessing safety of Leukine[®] [57], although the latest version of the NCI-CTCAE (Version 4.03) will also be referenced for all AE's (attached as Appendix F):

Anemia
Lymphopenia
Pain
Fever Flu-like symptoms
Arthralgia/myalgia
Injection-site reaction
Fatigue
Abdominal cramps
GERD/indigestion Insomnia
Cough
Sweating

Data and Safety Monitoring Board (DSMB):

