Atrophy in the Entorhinal cortex (ERC) and Hippocampus (HPC), measured on MRI scans, predicts future cognitive decline and conversion to AD among individuals with Mild Cognitive Impairment (MCI). Severity of MTA, assessed with MRI scans, is strongly associated with severity of medial temporal lobe degenerative pathology, especially the severity of neurofibrillary pathology, at autopsy.

HYPOTHESIS 3. Leukine[®] treatment in adults with mild-to-moderate AD will reverse or stop the progression of MTA.

EXPLORATORY AIM 1. To assess whether Leukine[®] treatment will improve specific cognitive domains in mild-to-moderate AD patients.

A battery of cognitive tests will be performed at baseline Day 1 and at approximately 15, 45, and 90 days after initiation of Leukine[®] treatment to determine whether any AD features reverse during or after Leukine[®] treatment compared to subjects receiving placebo. Secondary cognitive domain tests will include the ADCS-ADL (Alzheimer's Disease Cooperative Study Activities of Daily Living Inventory), Trail making tests (TRAILS) A, TRAILS B, Clinical Dementia Rating (CDR), and the Mohs Cancellation Task.

EXPLORATORY HYPOTHESIS 1. Leukine[®] treatment in adults with mild-to-moderate AD will improve specific cognitive domains as measured by the ADCS-ADL, TRAILS A,

TRAILS B, CDR, and the Mohs Cancellation Task.

EXPLORATORY AIM 2. To examine the effects of Leukine[®] treatment in mild-to-moderate AD patients on biomarkers associated with AD .

Biomarkers from peripheral blood collection include various forms of the hallmark proteins that form amyloid plaques in AD (i.e. amyloid-beta [A β] peptides), as well as other proteins which levels are known to be altered in AD (hyper-phosphorylated Tau and various inflammation-associated cytokines and chemokines).

EXPLORATORY HYPOTHESIS 2. Leukine[®] treatment in adults with mild-to-moderate AD will induce changes in blood biomarkers toward published control levels.

EXPLORATORY AIM 3. To determine if Leukine[®] treatment will change amyloid load in mild-to-moderate AD patients.

Amyloid PET scans will be performed using Pittsburgh Compound B (¹¹C-PiB), produced at the UCD-Anschutz Medical Campus (AMC) cyclotron laboratory, which allows for amyloid-beta neuritic plaque density imaging, and will be used to test the hypothesis that Leukine[®] treatment of mild-to-moderate AD subjects reduces cerebral amyloid load.

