Group comparisons of changes in regional volumes and thicknesses will be analyzed using a series of one-way analyses of variance (ANOVAs). The Scheffé post hoc procedure will be used to examine differences between means; Pearson product-moment correlation coefficients evaluated the strength of relationships between of changes in regional volumes and thicknesses and cognitive measures. Receiver operator curve analyses will determine sensitivity and specificity of various MTA cut points for distinguishing between diagnostic groups. Hazard ratios (HRs) for specific predictors of MTA progression and regression will be calculated using a three-state Markov model in continuous time. The proportional intensity model will be used to analyze effects of covariates on HRs.

Exploratory Aim 2: Levels of AD-associated biomarkers in blood will be compared between placebo controls and Leukine® treatment groups. The identification of circulating biomarkers in AD is a relatively new field, with inconsistent biomarker level results reported as increased, decreased, or unchanged between studies [37]. These mixed results mean that standardized levels for AD-associated circulating biomarkers have yet to be established. Therefore, we will compare observed biomarker levels from our project to other published levels to explore whether any similarities are observed. This comparison, as well as our own results, will add to the AD-associated blood biomarker field of literature.

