Once the results are available, if the subject continues to meet entrance criteria they will return for their baseline Day 1 (randomization) visit. This visit takes place about 1 to 4 weeks after the screen visit. At this visit, vital signs are recorded, 33 ml of blood will be drawn for a CBC with differential, a complete metabolic panel (CMP), and for biomarker assays (for example, GM-CSF, IFN- γ , IL-1 β , IL-2, IL-6, IL-8, IL-10, IL-12p70, TNF- α , Eotaxin, IP-10, MCP-1, MCP-4, MIP-1 β , TARC, P-Tau, Total Tau, and A β species), and tests of cognition, such as the MMSE, ADAS-cog, the ADCS-ADL scale, Trails A, Trails B, CDR, and the Mohs Cancellation task, are administered. The test article will then be delivered by the unblinded pharmacist, administered subcutaneously by the (blinded) study nurse or clinician, and the subject then goes home.

Subsequent injections will also be administered at the clinic. About 4 ml of blood will be drawn for CBC plus differential approximately every three days during the treatment phase to monitor for leukocytosis (see safety monitoring plan), and an additional 4 ml of blood will be drawn for CMPs once every week of the treatment phase. Vital signs, injection site review, and adverse events will be recorded at each visit. At the last treatment visit approximately three weeks later, we will record vitals, perform a physical exam, review for adverse events, administer cognitive tests and draw 33 ml blood for a CBC with differential, a CMP, and biomarker assays. A brain MRI will be done for comparison with the initial screen MRI to assess for any changes in the Medial Temporal lobe and for any incidence of vasogenic edema and microhemorrhage.

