Reporting mechanisms: AE forms will be completed and submitted on-line using the UCH AE reporting system. The report will include a description of the event, judgment as to whether or not it was related to study medication and the outcome of the AE.

Responsibility for preparing and submitting reports: The study coordinator will prepare the AE report and the Co-Principal Investigator will review/edit as appropriate and submit the AE.

Confidentiality Procedures:

The meetings of the **DSMB** will be closed to respect the privacy of the research participants. Data will be kept in case report binders in a locked cabinet when not in use. Data entered into the computerized data registry will only be accessible to those members of the research team.

Control of Conflict of Interest:

[name] was one of the conceivers of the Arthritis/GM-CSF/G-CSF approach to AD therapy and, along with [name], is one of the inventors on a University of South Florida patent on the use of GM-CSF in AD (US Patent 9,132,168) that is subject to the standard University of South Florida royalty sharing agreement. According to that agreement and although there are no current or immediately expected financial benefits that would attend the results of the proposed research, the University of Colorado Anschutz Medical Campus Conflict of Interest Committee (UCD-AMC COIC) has determined that Drs. [name] and [name] each have a significant financial interest due to the issuance of the patent, and the UCD-AMC COIC has approved management plans, which Drs. [name] and [name] will be glad to share upon request, and that allow the continued involvement of Drs. [name] and [name] in the clinical trials of Leukine. Additionally, the conduct of this trial will be further managed as follows: The Co-Principal Investigators, [name] and [name], who each have no real or perceived conflict, will carry out the clinical assessments of the subjects. Furthermore, the following steps will be used to help manage any potential conflict of interest:

- 1) The investigators will be blinded to the treatment group.
- 2) Endpoints are quantitative/objective (improvement in cognition by assessment with a battery of neuropsychological and clinical assessments used in the UCH clinic and changes in blood biomarkers towards normal).
- 3) If interested investigator(s) do participate in data collection and recording of data, they will be blinded and will not be the sole evaluator of the results/endpoints.

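### Exploratory Hypothesis 2 fixes no favourable direction for each biomarker, and its analysis leaves the Day 1 value unused and has no multiplicity rule

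*Combined protocol and SAP*

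**What the plan says.** Under Specific Aims, Exploratory Hypothesis 2 predicts that Leukine "will induce changes in blood biomarkers toward published control levels". It names no marker, reference source or time point. In Control of Conflict of Interest, item 2 lists "changes in blood biomarkers towards normal" among the endpoints described as quantitative and objective.

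The only analysis text for this aim is the Exploratory Aim 2 paragraph of the Data Analysis Plan. It says:

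- "Levels of AD-associated biomarkers in blood will be compared between placebo controls and" the Leukine groups.
- The field has "inconsistent biomarker level results reported as increased, decreased, or unchanged between studies", and "standardized levels for AD-associated circulating biomarkers have yet to be established".
- For that reason, "we will compare observed biomarker levels from our project to other published levels to explore whether any similarities are observed".

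Study Events provides for a baseline sample: on Day 1, "33 ml of blood will be drawn for a CBC with differential, a complete metabolic panel (CMP), and for biomarker assays". Biomarkers are drawn again at the last treatment visit and at both follow-up visits, and the study schedule table agrees. The Exploratory Aim 2 paragraph does not mention the Day 1 value, a model, a time point or a multiplicity rule.

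**The concern.** A prediction of movement toward control values needs a control value, or at least a direction, for each marker. The plan itself says the literature supplies neither consistently. Suppose one published study puts controls below patients on a cytokine and another puts them above. A Leukine-minus-placebo rise is then toward control by one source and away from it by the other, and nothing written in advance says which source governs.

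For a purely exploratory aim this would be a small matter. It carries more weight here because the conflict-of-interest section relies on this endpoint being objective as one way of managing the declared financial interest of two inventors. The assay is quantitative. The label of normalisation is not objective without a fixed reference. Blinding protects the measurement, but it does not protect a choice of reference made after unblinding.

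Two gaps in the analysis add to this. The hypothesis and the conflict-of-interest item speak of change while the analysis text speaks of levels, so a baseline already collected goes unused. And a large panel is measured repeatedly with no stated control of chance findings.

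**Working it through.** **The plan's own figures.** None is stated for the biomarker aim. The only sample-size table (Sample size considerations) concerns cognition, at alpha 0.20 and power 0.60. Exact t-test calculations reproduce it except for one entry: 2 per group rather than 3 for the one-tailed test at effect size 1.22. It does not bear on this point.

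**1. Direction.** The hypothesis and conflict-of-interest item 2 need a reference. The Exploratory Aim 2 paragraph says the references disagree and are not standardized, and it sets no criterion for similarity. These three places do not fit together.

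**2. Use of the baseline.** The MRI paragraph analyses changes in volumes and thicknesses. The PET paragraph takes each participant's difference between scans and then compares arms. The biomarker paragraph does neither.

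Illustration, with n = 20 per arm from Sample size considerations. Two-sided alpha 0.05, the true difference d in SD units, and the baseline-to-follow-up correlation r are assumptions. By normal approximation, power = Φ(d·√(n/2)/m − 1.96), where the SD multiplier m is:

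- post-treatment level only: 1
- change score: √(2(1 − r))
- ANCOVA on the Day 1 value: √(1 − r²)

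For d = 0.8, d·√(n/2) = 0.8 × √10 = 2.530, and level only gives Φ(0.570) = 72%.

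| r | Level only | Change score | ANCOVA |
|---|---|---|---|
| 0.3 | 72% | 57% | 76% |
| 0.5 | 72% | 72% | 83% |
| 0.7 | 72% | 90% | 94% |

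For d = 0.5, level only gives 35%, and ANCOVA gives 38%, 45% and 60% at the same three correlations. A plain change score beats the level comparison only when 2(1 − r) < 1, that is, r > 0.5. ANCOVA is better at every correlation tried.

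**3. Multiplicity.** The Bonferroni correction is stated in the paragraph for the Secondary Endpoint and Exploratory Aim 1 (cognition). The family-wise and false-discovery corrections are stated for PET. Neither covers the blood panel.

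Study Events names 17 analytes plus the Aβ species. Counting the latter as one gives 18, in a list offered only as examples. If each is tested at the three post-baseline visits at 0.05:

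- Tests: 18 × 3 = 54.
- Expected false positives if every null is true: 54 × 0.05 = 2.7, whatever the correlation.
- Chance of at least one, independent tests: 1 − 0.95^54 = 94%.
- Chance of at least one, by simulation with an assumed common correlation of 0.3, 0.5 or 0.8: 82%, 64% or 30%.
- One visit only, independent: 18 × 0.05 = 0.9 expected, and 1 − 0.95^18 = 60%.
- Counting one pre-set direction only (0.025 per test), independent: 1 − 0.975^54 = 75%, or 1 − 0.975^18 = 37% at one visit.

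**The case against.** The aim is labelled exploratory and is itself worded without a direction. The concurrent placebo comparison is the main analysis. Choosing a published reference afterwards cannot alter the between-arm difference; it alters only the description of its sign. The literature comparison is already framed as looking for similarities. Conflict-of-interest item 2 is one of eight measures, which include blinded investigators and no sole evaluator with an interest. All of this stands, and it keeps the point minor.

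The analysis paragraph can also be read as under-specified rather than as a decision to ignore the baseline, since it does not exclude adjustment. That is fair. It does not provide for adjustment either, although the neighbouring MRI and PET paragraphs specify change.

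The count of 54 is a construction. The plan does not say that every analyte will be tested at every visit, gives no alpha for this aim, and leaves the list open. The list includes GM-CSF, the administered drug, which is hardly a null test; without it, 17 × 3 = 51 tests give 51 × 0.05 = 2.55 expected and 1 − 0.95^51 = 93% if independent. The size is therefore conditional, but the absence of a rule is not.

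Two stronger readings are tempting. A reader might infer that the plan denies that published control levels exist. It does not: it calls them inconsistent and unstandardized, and it intends to compare with them. A reader might also infer that almost any result could be declared a success. The documents do not support that, because the randomized placebo comparison constrains what can be claimed.

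**Conclusion.** The point holds as a minor one, in three parts.

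- The favourable direction is not fixed for each marker, so the directional hypothesis and the objective label in conflict-of-interest item 2 are inconsistent with the analysis paragraph. This rests on the text alone.
- The level comparison is valid under randomization, but it is less precise than a baseline-adjusted one and is exposed to chance baseline imbalance at 20 per arm. In the illustration at 0.8 SD, ANCOVA raises power from about 72% to between 76% and 94%. The effect size, alpha and correlations are assumed. It would be wrong to infer that comparing levels is biased, or that a simple change score would be the remedy.
- No multiplicity rule covers the panel. Under the assumed 54 tests at 0.05, 2.7 false positives are expected, and the chance of at least one is about 30% to 94%. The 94% applies only if the tests are independent and should not be quoted alone.

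**What to change.** - Restate Exploratory Hypothesis 2 as a between-arm difference in each biomarker, adjusted for its Day 1 value.
- In the Exploratory Aim 2 paragraph, specify ANCOVA on the Day 1 value, on the log scale where the assay distribution is skewed. With Day 1 as covariate, the estimated treatment effect is the same whether the outcome is written as level or as change, which removes the mismatch in wording.
- List the analytes and visits that form the panel, and apply false-discovery-rate control over it at a stated level.
- Keep the comparison with published levels as description only.
- In Control of Conflict of Interest, item 2, replace "changes in blood biomarkers towards normal" with the between-arm biomarker difference.

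The cost is small changes of wording and analysis, with no new samples or assays, and fewer nominally significant exploratory results. The item 2 edit alters a conflict-of-interest statement as well as the analysis text, but the current amendment already updates that section. The introductory statement counts 30 participants through the treatment phase, so the changes should be made before any unblinded biomarker data are analysed.
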